## **6.2 Secondary Efficacy Endpoints and Analyses**

### **Assessment of clinical severity**

The NEWS will be calculated based on 7 clinical parameters and recorded on the eCRF. The

absolute value and change from baseline in the total score from Day 1 through Day 29 will be summarized by treatment group and visit using descriptive statistics.

Change in NEWS total score through Day 29 will be evaluated by fitting a linear mixed-effects model for repeated measures (MMRM). The model will include change from baseline in NEWS total score as the repeated dependent variable; treatment (as a class variable), visit (as a class variable), and treatment-by-visit interaction as fixed effects; baseline NEWS total score, age and gender as covariates; and measures within subject at each visit as a repeated measure. An unstructured covariance matrix will be used to model the within-subject error. If the fit of the unstructured covariance structure fails to converge, a compound symmetry covariance structure will be used. Parameters will be estimated using restricted maximum likelihood with the Kenward-Roger method for calculating the denominator degrees of freedom. Data collected starting at the Day 2 visit and up to the Day 29 visit will be included in this analysis. Missing data will not be imputed. From this model, the least-squares (LS) means and 95% CIs for each treatment group, the treatment difference in the LS means, the 95% CI for the difference, and the associated p-value will be reported on Days 15 and 29, as well as for the average across all post-baseline visits.

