#### **2.1.2 Secondary Efficacy Objectives**

To compare Liquid Alpha1-PI plus SMT versus placebo plus SMT with regard to clinical efficacy as assessed by clinical severity, duration of hospital stay, dependency on oxygen or new need for ventilatory support, clinical response criteria including National Early Warning Score (NEWS) and clinical status scale through Day 29 in hospitalized subjects with COVID-19.

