## 3.2 Treatment

### 3.2.1 Randomization Scheme and Treatment Arm Assignment

Subjects will be randomized 1:1 to receive either combination treatment with Liquid Alpha1-PI (Human) plus SMT or placebo plus SMT.

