## 4. GENERAL CONSIDERATIONS FOR DATA ANALYSIS

Unless otherwise specified, continuous variables will be summarized using descriptive statistics

(n, mean, standard deviation, median, minimum, and maximum). Categorical variables will be summarized showing the number and percentage of subjects within each category.

Summary results will be provided for each treatment group. All tabulations will be based on pooled data across centers.

All statistical tests will be two-sided and tested at the 5% level of significance.

Analyses will be performed using SAS for Windows statistical software, version 9.4 or higher (SAS, Cary, NC), except where other software may be deemed more appropriate. In the event that other software is used to perform some analyses, the details will be provided in the Clinical Study Report.

██████████ will perform all efficacy and safety analyses described in this SAP and Grifols will review them.

Subject data will be listed, sorted by treatment group and subject number. When applicable, listings will be additionally sorted by visit and assessment date/time.

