#### 4.4 Handling of Dropouts or Missing Data

Missing data will be treated as missing and no method for imputation is planned for study population or safety analyses except for the partial end dates/times for concomitant medications (Section 5.6) and partial onset dates/times for AEs (Section 7.2.1). When applicable, missing data for binary and selected continuous efficacy endpoints will be imputed using a most conservative/worst case approach, and the related details are described in Section 6.

Time to event endpoints will have events coded as right censored or competing events per the following table:

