## 6. EFFICACY ANALYSES

All efficacy analyses will be carried out using the ITT population. Data on all efficacy endpoints will be listed and tabulated if appropriate.

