### **Duration of Hospitalization**

The duration (number of days) of hospitalization from Day 1 through Day 29 will be calculated based on hospital admission and discharge dates recorded on the eCRF. Number of days in the hospital will be compared between treatment groups using an ANOVA model, including number of days in the hospital as a dependent variable and treatment group as a fixed effect. From this model, the LS means and 95% CIs for each treatment group, the treatment difference in the LS means, the 95% CI for the difference, and the associated p-value will be presented. If appropriate, an ANCOVA model may instead be used to additionally adjust for baseline characteristics such as age and gender.

Subjects who died while in the hospital will be assigned as in the hospital for the number of days remaining from the day of death to Day 29 for the analysis. Subjects who were in the hospital at

study completion will be assigned a hospitalization end date equals to the date of completion for the purpose of deriving the duration of hospitalization.

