## 9. SAMPLE SIZE AND POWER CALCULATIONS

Because of the urgency and lack of previous prospective COVID-19 data, sample size estimation remains incompletely defined; however, the size of this pilot study is commensurate with other Phase 2 investigations ongoing during the COVID-19 pandemic. Approximately 100 subjects are allowed to be randomized as part of a humanitarian effort against COVID-19.

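### The NEWS mixed model estimates change in NEWS as if no subject had died, so a halving of deaths can show as no effect or as slight harm on this secondary endpoint

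*SAP*

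**What the plan says.** SAP 6.2 (Assessment of clinical severity) fits a repeated-measures mixed model to change in NEWS. It has treatment, visit, their interaction, baseline NEWS, age and gender, and is estimated by restricted maximum likelihood. The covariance is unstructured, with compound symmetry as the fallback. On incomplete data it rules out imputation: "Data collected starting at the Day 2 visit and up to the Day 29 visit will be included in this analysis. Missing data will not" [...]. LS-mean differences are reported at Days 15 and 29 and averaged over post-baseline visits.

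SAP 6 states: "All efficacy analyses will be carried out using the ITT population". Subjects who die are therefore in the analysis set. Protocol Appendix 2 builds NEWS from seven bedside items and gives no points for death. Neither document assigns a NEWS value or rank after death or plans a sensitivity analysis for it.

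Elsewhere the SAP does deal with death. For days in hospital, the rule runs up to Day 29: "Subjects who died while in the hospital will be assigned as in the hospital for the number of days remaining from the day of death". ICU, oxygen and ventilation days have similar rules, discharge treats death as a competing event, and death is the lowest category of the ordinal scale. SAP 4.4 says that, where applicable, "missing data for binary and selected continuous efficacy endpoints will be imputed using a most conservative/worst case approach", and leaves the details to Section 6. SAP 8.2 lists NEWS change among the secondary outcomes for the futility review and plans no sensitivity analyses there.

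**The concern.** A likelihood mixed model with no imputation treats every visit after death as missing at random. In effect it continues each deceased subject's course with the NEWS of a living patient, predicted from that subject's earlier readings and the arm's means. The resulting contrast asks what NEWS would have been had no one died. The secondary objective in SAP 2.1.2 is "clinical efficacy as assessed by clinical severity", among other measures, through Day 29 in the hospitalised subjects. Death is the most severe outcome in that population and part of the primary endpoint.

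If treatment keeps alive subjects who remain ill, their high scores enter the active arm. Their placebo counterparts die and leave the data. A real survival benefit can then vanish from this endpoint or change sign. A reader of the final report, or the unblinded team at the futility review, could take a flat NEWS result as evidence against the drug when it partly reflects who survived to be scored.

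**Working it through.** **Inputs from the documents**
- Test level, SAP 4: "All statistical tests will be two-sided and tested at the 5% level of significance".
- Size, SAP 9: "Approximately 100 subjects are allowed to be randomized as part of a humanitarian effort against COVID-19".
- Allocation, SAP 3.2.1: "Subjects will be randomized 1:1 to receive either combination treatment". Hence about 50 per arm.
- NEWS maximum, from the Appendix 2 items: 3+3+2+3+3+3+3 = 20.

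The plan states no power, effect size, SD or death rate, so there is no figure to reproduce.

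**Assumptions (not in the documents)**
- Baseline NEWS is 5 (SD 2). The mean at day d is 5 - 4(1 - exp(-d/8)), about 1.1 at Day 29.
- Control deaths are 10%, 20% or 30%, halved on active, and fall on Days 3 to 27.
- A: NEWS while alive is unrelated to death or treatment.
- B: NEWS rises by up to 6 before death, and saved subjects recover normally.
- C: as B, but saved subjects stay 6 points higher.

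**Hand check with death scored 20**

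Day 29 difference (active minus placebo, negative favours active) = (reduction in deaths) x (saved subjects' NEWS - 20).
- A and B: 0.05 x (1.1 - 20) = -0.95; 0.10 x (-18.9) = -1.89; 0.15 x (-18.9) = -2.84.
- C (saved subjects at about 7.1): 0.05 x (-12.9) = -0.65; 0.10 x (-12.9) = -1.29; 0.15 x (-12.9) = -1.94.

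**Simulation of the planned model**

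50 per arm, 200 trials per row, visits on Days 2, 3, 4, 5, 8, 10, 15 and 29, NEWS missing after death. Rejection rates are in brackets. The last column is a simple difference in means.

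| Scenario, deaths | Unstructured, Day 29 | Compound symmetry, Day 29 | Death = 20, Day 29 |
|---|---|---|---|
| A, 10% to 5% | 0.00 (5%) | 0.00 (3%) | -0.88 |
| A, 20% to 10% | 0.01 (4%) | 0.01 (2%) | -1.93 |
| A, 30% to 15% | -0.05 (4%) | -0.04 (2%) | -2.79 |
| B, 10% to 5% | -0.07 (6%) | -0.08 (4%) | -0.95 |
| B, 20% to 10% | -0.22 (7%) | -0.24 (4%) | -1.94 |
| B, 30% to 15% | -0.29 (14%) | -0.33 (9%) | -2.94 |
| C, 10% to 5% | +0.14 (7%) | +0.15 (5%) | -0.71 |
| C, 20% to 10% | +0.31 (7%) | +0.39 (14%) | -1.22 |
| C, 30% to 15% | +0.43 (14%) | +0.63 (27%) | -1.92 |

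The planned model shows nothing in A. In B the unstructured fit keeps 0.07/0.95 = 7%, 0.22/1.94 = 11% and 0.29/2.94 = 10% of the death-counted difference. In C it points the wrong way.

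The sign in C is easy to see at 20% vs 10%. Among subjects alive on active, 0.10/0.90 are saved and 6 points higher, so the raw survivor means differ by 0.10 x 6/0.90 = +0.67. The model corrects only part of that.

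**Other assumptions**

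A separate simulation used 2,500 per arm and compound symmetry, with NEWS rising to about 9.5 before death. For deaths of 20% vs 10%, 10% vs 5% and 15% vs 10%:
- Saved subjects ill at about 7: +0.08, +0.01 and +0.02, against -1.26, -0.64 and -0.63 with death = 20.
- Saved subjects recover: -0.52, -0.20 and -0.17, against -1.87, -0.90 and -0.78. It keeps 28%, 22% and 22%, more than in B above.

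**Limits**

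The first simulation used maximum likelihood without Kenward-Roger, no age or gender, eight visits and no missing data other than after death. The second omitted age and gender.

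**The case against.** - **The size depends on the yardstick.** This stands. With saved subjects near 7 and a 10-point fall in mortality, about 0.10 x (20 - 7) = 1.3 points come directly from scoring death as 20. The gap is between two estimands, and the mortality and NEWS courses are assumed.
- **Death-inclusive severity is already planned.** This largely stands. SAP 6.2 compares ordinal-scale categories at Days 15 and 29 with death as category 1. Death also counts in the primary endpoint, clinical progression and the duration endpoints. None of this tells the reader of the NEWS table what its own estimate means.
- **A reader might infer that SAP 4.4 is breached.** It is not. It promises worst-case handling only where applicable and for selected continuous endpoints, and Section 6.2 expressly declines imputation for NEWS. Nor is worst-case the SAP's uniform rule for death: Table 1 censors deaths in time to clinical response.
- **A reader might infer that excess deaths on active would be hidden.** The documents do not support that. Adverse events leading to death are tabulated by arm (SAP 7.2.5), and each death pauses enrolment for committee review (Protocol 8.5).
- **A worst-rank Wilcoxon test would not rescue the hardest case.** This stands. At 20% vs 10% with saved subjects still ill, the win probability is 0.2 x 0.95 + 0.8 x 0.8 x 0.5 = 0.51. Simulated values for 20% vs 10%, 10% vs 5% and 15% vs 10% were 0.515, 0.504 and 0.506, with rejection of 5-6%.
- **The consequence is limited.** This stands. The endpoint is one of several exploratory secondaries without multiplicity adjustment. Futility rests on conditional power for the primary outcome plus an unstructured look at the secondaries, with no NEWS threshold. No changed decision has been shown.

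**Conclusion.** The concern holds for this endpoint. As written, the NEWS model gives an as-if-nobody-died contrast, and the SAP neither says so nor offers one that counts death. That conclusion follows from the text and needs no assumed figures.

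The magnitudes do need them. Under the assumptions above, halving deaths gave a Day 29 difference near zero when NEWS in life was unaffected. It gave a small fraction of the death-counted difference when saved subjects recovered, and a slight difference towards harm when they stayed ill under the first simulation's assumptions. These figures are illustrations, not estimates for this trial.

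The effect is on the interpretation of one secondary endpoint and its part in the futility review. It does not touch the primary test. The ordinal-scale, duration and safety analyses still show deaths.

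**What to change.** In SAP 6.2, and in the Section 8.2 outputs:
- Add a NEWS comparison at Days 15 and 29 that counts death, by entering 20 from the day of death through Day 29 and refitting the same model.
- Keep the present model and label it as hypothetical (as if no deaths).
- Show the number of deaths per arm beside each LS-mean difference.
- Optionally add a worst-rank Wilcoxon test as a check, noting its low sensitivity when saved subjects remain ill.
- Amend the statement in Section 8.2 that no sensitivity analyses are planned, so that the added output is permitted.

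The cost is SAP wording and one more programmed analysis. Dates of death are already used to derive clinical progression (SAP 4.6), so no new data or subjects are needed. The downside is that 20 is a convention that drives the size of the difference, so the result should be read beside the death counts and not as NEWS points alone. Power stays modest: in scenario A a t-test with death scored 20 rejected in 11%, 28% and 45% of trials, close to the 15.5%, 28.6% and 43.4% power for the death contrast itself. The reason for the change is to answer the stated question, not to gain power.

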### **Time to clinical response**

Clinical response is defined as the NEWS score <=2 maintained for 24 hours from Day 1 through Day 29. The time to the first occurrence of clinical response will be estimated using the Kaplan-Meier (KM) method. The KM estimates along with 95% CI, and survival curves will be provided. Based on the KM estimates, the probabilities of achieving first clinical response and associated 95% CIs on Days 15 and 29 will be reported; in addition, the 25th, 50th (median), and 75th percentiles of the time to first clinical response with associated 95% CIs will be provided, as data permit. The survival rates between treatment groups will be compared using Log-rank test. The p-value from Log-rank test will be presented.

### **Time to hospital discharge**

Time to hospital discharge is defined as duration of hospitalization from Day 1 through Day 29. The proportion of subjects who are discharged from the hospital will be estimated using the CIF. Deaths that occur prior to discharge from the hospital will be treated as a competing risk. The estimated cumulative incidence and associated two-sided 95% CI on Days 15 and 29 will be displayed. Test for equality of the CIF between treatment groups will be conducted using Gray's test.

### **Duration of Hospitalization**

The duration (number of days) of hospitalization from Day 1 through Day 29 will be calculated based on hospital admission and discharge dates recorded on the eCRF. Number of days in the hospital will be compared between treatment groups using an ANOVA model, including number of days in the hospital as a dependent variable and treatment group as a fixed effect. From this model, the LS means and 95% CIs for each treatment group, the treatment difference in the LS means, the 95% CI for the difference, and the associated p-value will be presented. If appropriate, an ANCOVA model may instead be used to additionally adjust for baseline characteristics such as age and gender.

Subjects who died while in the hospital will be assigned as in the hospital for the number of days remaining from the day of death to Day 29 for the analysis. Subjects who were in the hospital at

study completion will be assigned a hospitalization end date equals to the date of completion for the purpose of deriving the duration of hospitalization.

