- Screening/Baseline (Day 1) during which eligibility criteria are reviewed. Once all eligibility criteria are met and all pre-infusion assessments are completed, blinded Liquid Alpha₁-PI (Human) or Placebo administration can begin as expeditiously as feasible. On Day 8 a second IV dose of blinded Liquid Alpha₁-PI (Human) or Placebo will be administered on Day 8. If the subject has been discharged from the hospital at the time of the Day 8 blinded Liquid Alpha₁-PI (Human) or Placebo infusion, the 2nd infusion is not mandatory, and is at the discretion of the Principal Investigator and subject.
- SMT, Observations, and Follow-up (Days 2 to Day 29): SMT will be provided to all subjects with daily assessments while hospitalized and follow-up from Day 2 through Day 29±1 day (inclusive).
- Phone Checks will occur at Day 60 and Day 90 for vital status (living or deceased), any hospital re-admissions or serious/non-serious adverse events after the Day 29 Final Clinic Visit.

The overall study schema is shown in [Figure 4-1](#).

GRIFOLS	Number	BIG-CL-PRT-000019	Version	6.0	Status	Effective	Effective Date	08-Dec-2021
	GC2006 -A Multicenter, Randomized, Open-label, Parallel Group Pilot Study to Evaluate the Safety and Efficacy of Prolastin®-C Liquid plus Standard Medical Treatment (SMT) versus Bioscience Industrial Group							
								38 of 94

IV = intravenous; SMT = standard medical treatment

*Note: If the subject has been discharged from the hospital at the time of the Day 8 blinded Liquid Alpha-1 PI infusion, the 2nd infusion is not mandatory, and is at the discretion of the Principal Investigator and subject

Figure 4-1 Overall Study Schema

GRIFOLS Bioscience Industrial Group	Number	BIG-CL-PRT-000019	Version	6.0	Status	Effective	Effective Date	08-Dec-2021
	GC2006 -A Multicenter, Randomized, Open-label, Parallel Group Pilot Study to Evaluate the Safety and Efficacy of Prolastin®-C Liquid plus Standard Medical Treatment (SMT) versus SMT alone in Hospitalized Subjects with						Page	39 of 94

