Record oxygen saturation (specify on or off oxygen supplementation)	X		X	X	X	X	X	X	X	X	X	X	X	X	X		
Randomization (after all Screen/Baseline assessments complete)	X																
IV dose of blinded Liquid Alpha₁-PI (Human) 120 mg/kg body weight (or Placebo) given on Day 1 and Day 8		X										X ^k					
Record hospital admission and discharge dates	X														X ^f		
If subject requires ICU admission post randomization: Record ICU admission & discharge dates															X ^f		
Assessment of ARDS (Berlin Criteria) (Appendix 3)	X					X						X		X			
Respiratory sample for quantitative measurement of SARS-CoV-2 viral load by NAT or PCR (real-time RT-PCR) (obtained via nasopharyngeal swab)	Pre randomized treatment ^g					X						X		X			
Sample for quantitative measurement of IgM and IgG antibodies to SARS-CoV-2 (if antibodies cannot be determined quantitatively store serum samples frozen at -70°C for later analysis at an external lab)	Pre randomized treatment ^g					X						X		X			

CONFIDENTIAL

Study Period	Screen/ Baseline	IP	SMT and Daily Evaluations ^j								Follow-Up	Follow-Up Clinic Visit Day				
			2	3	4	5±1 ^m day	6	7	8	9		15± 1 day ^m	16-28 Daily if in hospital	29 ^e ± 1 day ^m	Day 60 ± 2 days	Day 90 ± 2 days
Procedures/assessments	Study Day	1	1 st IP infusion day				X						X		X	
Serum Chemistry (creatinine, albumin, alanine aminotransferase [ALT], total bilirubin, lactate dehydrogenase [LDH])		Pre randomized treatment ^g														
Calculate an estimated glomerular filtration rate (eGFR) using the Cockcroft-Gault formula		Pre randomized treatment ^g				X						X		X		
Ferritin, CRP, D-dimer		Pre randomized treatment ^g				X						X		X		
Hematology & absolute neutrophil & lymphocyte count (hemoglobin, hematocrit, platelet count, leukocyte count with differential)		Pre randomized treatment ^g				X						X		X		
Cytokine panel ^h		Pre randomized treatment ^g				X						X		X		
Levels of alpha 1-PI (AAT) activity and antigen (both plasma [sodium citrate] and serum samples to be stored for measurement of both antigenic content and functional activity [potency])		Pre randomized treatment ^g							X ^{gi}			X		X		
Record SAEs and TEAEs ^d		X	X	X	X	X	X	X	X	X	X	X	X	X	X	
Record standard care concomitant medications		X	X	X	X	X	X	X	X	X	X	X	X	X	X	
Phone Checks for Vital Status (living or deceased), any hospital re-admissions or SAEs/non-serious AEs after Day 29 Final Clinic Visit															X	X

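### Hospital days are filled to Day 29 only for deaths in hospital, so a death at home after discharge is scored as a short stay

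*SAP*

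**What the plan says.** Two secondary endpoints in SAP 6.2 describe time in hospital.

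- **Duration of Hospitalization.** The number of days from Day 1 through Day 29 "will be calculated based on hospital admission and discharge dates recorded on the eCRF" and is compared between arms by ANOVA. SAP 4.6 defines a duration as end date minus start date plus 1. Deaths have one rule: "Subjects who died while in the hospital will be assigned as in the hospital for the number of days remaining" up to Day 29. A subject still in hospital at study completion gets the completion date as end date. Nothing is said about a death after discharge, or about a second stay.
- **Time to hospital discharge.** This is analysed by cumulative incidence with Gray's test. "Deaths that occur prior to discharge from the hospital will be treated as a competing risk". SAP Table 1 censors only subjects who were never discharged during follow-up. Any discharge is therefore an event, and no later occurrence reverses it.

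On data collection, the row "Record hospital admission and discharge dates" in Protocol Appendix 1 is marked at baseline and at Day 29. Readmissions are named only for the Day 60 and Day 90 telephone checks, which ask about "any hospital re-admissions or serious/non-serious adverse events after the Day 29 Final Clinic Visit".

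**The concern.** The fill to Day 29 stops an early death from looking like a quick recovery. It depends on where the subject died, so a death at home after a short stay escapes it and is ranked with the best outcomes on the duration endpoint. The same subject also remains a discharge success in the cumulative incidence analysis.

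If one arm discharged earlier and had more deaths after discharge, both endpoints would lean towards that arm. Time to discharge and duration of hospitalization are both on the list of outcomes for the interim futility analysis (Protocol 9.3, SAP 8.2), so the scoring could also colour that review.

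A related gap is that the SAP does not say how hospital days are counted when a subject has more than one stay before Day 29.

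**Working it through.** The documents give no figure for this endpoint (no expected mean, SD or event rate), so there is none to reproduce. The check applies the SAP's rules to example subjects.

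**Inputs**
- Duration = end − start + 1 (SAP 4.6), with start at Day 1.
- Fill to Day 29 for in-hospital death only (SAP 6.2).
- Size: "Approximately 100 subjects are allowed to be randomized as part of a humanitarian effort against COVID-19" (SAP 9), and "Subjects will be randomized 1:1 to receive either combination treatment" (SAP 3.2.1), hence about 50 per arm.
- Example days and counts of subjects are assumptions for illustration.

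**Step 1. The same death in two places**
- Discharged Day 4, dies at home Day 12: 4 − 1 + 1 = **4 days**, and a discharge event.
- Still in hospital, dies Day 12: 12 − 1 + 1 = 12, plus 29 − 12 = 17 remaining days, total **29 days**, and a competing event.
- Gap: 29 − 4 = 25 days. In an arm of 50: 25 / 50 = **0.5 day per subject**.

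The gap depends on the day of discharge: Day 5 gives 29 − 5 = 24 (0.48 day), Day 8 gives 21 (0.42 day), Day 15 gives 14 (0.28 day).

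**Step 2. Several such subjects in one arm and none in the other**

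| Subjects (assumed) | Difference in arm mean, 25 days each | Day 29 discharge incidence if not counted as success |
|---|---|---|
| 1 | 0.5 day | −2 points |
| 2 | 1.0 day | −4 points |
| 3 | 1.5 days | −6 points |
| 5 | 2.5 days | −10 points |

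Only an imbalance biases the comparison; equal numbers with equal gaps cancel in the mean difference. For scale, an assumed SD of 7 to 10 days gives a standard error of the difference of SD × √(2/50) = 1.4 to 2.0 days. One unmatched subject is then 0.5/2.0 = 0.25 to 0.5/1.4 = 0.36 of a standard error.

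**Step 3. What the proposed rule would give**

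Adding the days after death (Days 13 to 29) to the at-home death gives 4 + 17 = 21 days, or 22 if the day of death is also counted. The score rises by 17 or 18 days, or 0.34 or 0.36 day in the arm mean. The rest of the 25-day gap is time alive outside hospital, which is properly not counted.

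**Step 4. Readmission**

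Discharge on Day 4 with a second stay on Days 7 to 25:
- first stay only: 4 days;
- sum of stays: 4 + (25 − 7 + 1) = 4 + 19 = 23 days;
- first start to last discharge: 25 days.

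The SAP does not choose among these. The discharge event at Day 4 stands under all three.

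**The case against.** The best defence is that the endpoint is days in hospital, and a subject who went home on Day 4 spent 4 days there. ICU days have the same location-based rule. First discharge with pre-discharge death as a competing risk is a coherent estimand, and statisticians differ on whether sustained discharge is better. Post-discharge deaths are penalised elsewhere: the primary composite (SAP 6.1) counts a recorded death with no in-hospital restriction, and time to progression and the ordinal scale also count death.

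Most of this stands. It supports keeping first discharge as the event and limits the point to secondary endpoints. It does not rescue the duration rule: by filling days after an in-hospital death, the SAP has already given up the literal count, and it then treats the same outcome differently by place of death.

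A reader might infer more than the documents support:

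- **That readmission before Day 29 never lengthens hospital days.** The SAP is silent, and a count of days in hospital from eCRF dates is compatible with summing stays.
- **That any readmission or death after discharge is missed.** Read literally, death during a readmission is a death in hospital, so the fill applies. A subject back in hospital at study completion is covered by the completion-date rule.
- **That readmissions before Day 29 are not captured.** The eCRF is not shown. SAP 6.1 and 6.2 refer to an all-visits page on hospitalization. Admissions of 24 hours or more can meet the seriousness criteria (Protocol 8.3.7) and so be recorded as SAEs, though COVID-19 symptoms generally are not recorded as individual TEAEs. Capture is unconfirmed, not shown to be absent.
- **That the rule contradicts the SAP's worst-case approach.** SAP 4.4 applies that approach to missing data. A completed stay followed by death at home has no missing discharge date.

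**Conclusion.** The point holds for death outside hospital after discharge. As written, SAP 6.2 scores it as a short stay: 4 days against 29 in the example, worth 0.5 day in the mean of an arm of 50 for each such subject. The total effect cannot be given, because the documents state neither how many such deaths to expect nor an SD; the counts in the table are assumptions.

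For readmission, the finding is a missing counting rule and an unconfirmed data item, not a demonstrated error. For time to discharge, the first-discharge event is acceptable but should be tested in a sensitivity analysis. The primary endpoint is untouched. The affected outcomes are secondary, but they are among the inputs to the futility review, so the rule should be settled before unblinded data are examined.

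**What to change.** 1. In SAP 6.2, Duration of Hospitalization, extend the death rule: for any death on or before Day 29, wherever it occurs, the days from death to Day 29 are assigned as hospital days. Say whether the day of death is included.
2. In the same section, state that in-hospital days are summed over all stays from Day 1 to Day 29. Confirm that the eCRF captures readmission and later discharge dates before Day 29, and add the item if it does not.
3. In SAP 6.2, Time to hospital discharge, keep first discharge as the event. Add a sensitivity analysis in which a discharge followed by death or readmission by Day 29 is not counted as a success.

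The cost is a few sentences in the SAP, a little extra analysis work and possibly one eCRF item. The duration endpoint will then mix deaths outside hospital with days in hospital, as it already does for deaths in hospital.
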